- Mortality at D90
- Neurological functional status at D90
- Assessment of the patient's quality of life at D90
- Assessment of patient autonomy at D90
- Neurocognitive assessment of the patient at D90
- Estimation of the number of patients with post-traumatic stress symptoms at D90
- Length of stay in intensive care
- Duration of mechanical ventilation
- Need for vasopressor treatment in the first 72 hours

IV. Research design

A. Precise statement of primary and, where appropriate, secondary evaluation criteria

1. Primary endpoint

- Changes in serum levels of IL6 (inflammation marker) over the 48 hours following achievement of the thermal target (33°C) according to 2 reheating modalities during a targeted thermal control between 32.5° and 33.5°C: group with a slow reheating rate (RL; 0.25°C/h) compared with a group with a high reheating rate (RR; 0.5°C/h).
 - The choice of IL6 is based on the fact that it is one of the main interleukins produced during the inflammatory process. Several studies have demonstrated a strong correlation between IL6 levels and the neurological outcome of patients suffering cardiac arrest (57, 58). In addition, a description of the variations in IL6 during the performance of a 32.5-33.5 CCT after cardiac arrest has been carried out, making it possible to formulate the hypotheses necessary for calculating the number of patients in a cardiac arrest. (59).
 - H0 will be defined as the time at which the thermal target is reached, i.e. a body temperature of 33°C. This definition will make it possible to compare variations in inflammatory cytokines linked to rewarming rates and not to variations linked to the different times at which RTAs occur.
 - Given the high number of infectious complications expected (i.e. inhalation pneumonitis (49, 60)), given that it is not possible to perform a stratification on this pathology which nevertheless modifies the rates of IL6 (57) A record of these complications will be included in the data collection medium in order to ensure the homogeneity of the 2 groups of patients for these pathologies. Nevertheless, the diagnostic hypotheses take account of this high rate of infectious complications, since in the study used to formulate these hypotheses, patients who presented an infectious complication were included. (59). As for late complications, they may be linked to the rate of rewarming drawn at random by analogy with the infectious risk of hypothermia (61).

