Randomisation will be carried out within a 6-hour time window, the end of which will be determined by the 24^{ème} hour after the target temperature of 33° is reached (i.e. H24). This time window will therefore be between H18 and H24. This method will make it possible not to randomise patients

who have had an unfavourable outcome between inclusion and the start of the rewarming period (death following a refractory state of shock). This randomisation will be carried out via computerised data collection (eCRF): the patient will then be assigned to a randomisation arm: RL group or RR group.

b) Performing sedation/analgesia

This sedation/analgesia will be carried out in the 2 groups (RR and RL) during the period of hypothermia and rewarming until a temperature of 36°C is reached:

- Continuous administration of a hypnotic (midazolam, propofol) at a titrated dose to obtain a RASS score of -5 in both groups.
- Continuous administration of a morphine (fentanyl, sufentanil, remifentanil) at a titrated dose to obtain a RASS score of -5 and the absence of painful symptoms using the usual scales (behavioural pain scale) in the 2 groups.

This sedation/analgesia will be discontinued once a temperature of 36° Celsius has been reached.

In the event of haemodynamic, respiratory or neurological instability (agitation, risk of self-extubation in particular), this sedation/analgesia may be continued beyond this period. This continuation will be recorded in the eCRF.

c) Shiver management strategy

In accordance with the published protocol for the intensive care unit at La Roche Sur Yon (78) the treatment strategy for shivering will initially be based on boluses of hypnotics and morphine, followed by curare as a last resort (50, 79). The severity of shivering should be assessed using the Bedside Shivering Assessment Scale (see appendix C), which has been validated and is correlated with the increase in metabolic demand associated with shivering phenomena (80). The aim is to obtain a BSAS score ≤ 1 .

- Level 1 treatment for chills :
 - A bolus corresponding to a dose equal to the flow rate of the electric syringe administering the continuous infusion of the hypnotic and morphine administered (e.g. for an electric syringe flow rate of 5mg/h, a bolus of 5mg of the product concerned will be injected).
- Level 2 treatment for chills :
 - After failure of level 1

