b) Patient follow-up

Analyses will be carried out locally or off-site depending on the examinations concerned:

Off-site analyses (CHU Nantes): II2, II4, II6, II8, II10, GM-CSF, TNF-alpha, INF-beta, neurofilament. All these analyses can be performed using a 5 ml blood tube for all the analyses (i.e. a total of 60 ml of blood taken, taking into account the safety sample kept on the investigator's site). The principles of the LuminexTM assay and the Patrol test are explained in appendix J.

Local tests: blood count, arterial blood gases (pH, pO₂, pCO₂, HCO₃), lactates, blood ionogram (Na, K, Cl, Urea, Creatinemia, Ca), troponin, CRP, procalcitonin.

Local examination: 12-lead electrocardiogram

Neurological analysis using the CPC score will be carried out by telephone by an expert blinded to the randomisation group (psychologist carrying out a semi-directive interview, blinded to the randomisation group).

Flow Chart :

	Inclusion	J0	J1	J2	Jn	J90
Eligibility: check the study's eligibility criteria	X					
Informing the next of kin with a cooling-off period	X					
No-objection search	X					
Demographic data	X					
Randomisation		X				
Patient characteristics	X					
Data : coronary angiography	X					
Data: ventilation	X	X	X	X	X	
Biology	X	X	X	X		
Electrocardiogram	X		X	X		
Clinical evaluation	X		X	X	X	X
Treatments administered		X	X	X	X	
Definitive extubation					X	X
Living / Deceased		X	X	X	X	X
Blind neurological assessment by a psychologist						X

D0 corresponds to the start of the hypothermia procedure.

Jn corresponds to discharge from intensive care

B. Description of measures taken to reduce and avoid bias

1. Prize draw

This randomisation will be carried out directly on the electronic observation notebook provided (see Data collection). Randomisation will be carried out according to a 1:1 ratio with blocks of variable size, as the study will be open-label. No stratification factors will be taken into account. Randomisation will be generated by the CIC INSERM 1415 biometrics unit, which is independent of the patient recruitment process. It will be carried out within a time window of 6 hours, the end of which will correspond to the end of the CCT 32.5-33.5 period (i.e. between H18 and H24). This delayed randomisation will allow only patients alive at the end of the 32.5-33.5 CCT period to be randomised, and not patients who died during the first phase (e.g. progressing to refractory shock).

2. Blinding method

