As this is a routine care study, all the drugs normally used in the management of intensive care patients will be used according to the specific needs of each patient.

D. *Unauthorised treatments*

As this is a routine care study, no drugs used in its indication are prohibited.

IV. Safety assessment

A. *Independent Supervisory Committee*

No independent monitoring committee is planned as part of this study.

B. *Undesirable effects*

The occurrence of an Adverse Reaction linked to the patient's care during the course of this protocol will give rise to a declaration to the appropriate vigilance system (pharmacovigilance, biovigilance, haemovigilance, materialovigilance, etc.).

C. *Management of expected adverse events in the 2 randomisation groups*

a) Death, including death following a procedure to limit or stop treatment

Deaths following a procedure to limit or stop treatment will be recorded in the computerised eCRF database, together with the characteristics describing the reasons for the decision. For information, investigators will be provided with the opinion of the SRLF ethics committee concerning the decision to limit or stop treatment in adults in post-anoxic coma following cardiac arrest. (97).

b) Inhalation pneumonitis

A procedure of recommendations for use by the doctors in charge of the patient will be made available to them, including the anamnestic, clinical, biological and radiographic data that should suggest inhalation pneumonitis, together with a recommendation for antibiotic therapy in line with expert recommendations. (98).

c) Hypovolaemia

A haemodynamic assessment will be carried out to optimise the patient's blood volume. In the event of hypovolaemia, vascular filling will be carried out using crystalloids or colloids in accordance with the department's usual practices. The patient's haemodynamic status will be reassessed as required. In accordance with recommendations, and in the absence of specific studies, a mean arterial pressure target of 65 mmHg and, if used, a ScvO₂ greater than or equal to 70% will be considered reasonable targets (31, 32). The introduction of treatment with vasoactive amines should be left to the clinician's discretion, in accordance with international recommendations (31, 32).

d) Electrocardiographic changes: prolongation of PR and/or QT interval

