The primary endpoint will be analysed using a linear mixed model. If necessary, the data will be transformed beforehand.

Analysis of secondary endpoints

Secondary endpoints associated with a binary variable will be analysed using Fisher's exact test.

Secondary endpoints associated with a quantitative variable will be analysed using the same strategy as for the primary endpoint, using Student (or Wilcoxon) tests if the data are not repeated.

Finally, the parameters of the repeated measurements will be analysed using mixed models.

B. *Expected number of people to be included in the research, and expected number of people in each research location with statistical justification*

The headcount calculation is based on the work of Borm (99) and Vickers (100).

In this trial, the primary endpoint (interleukin 6 levels) is measured repeatedly. To calculate the number of patients required, the following parameters are required:

- The standard deviation of the interleukin 6 assay was set at 40 pg/ml.
- The main hypothesis is that a high heating rate ($>0.5^{\circ}\text{C}/\text{h}$) leads to an increase in inflammatory phenomena measured by IL6. In this case, according to previous studies (101) the mean level of IL6 expected in the slow rewarming group will be 100 pg/ml.
- A 15% increase (superiority analysis) in these phenomena is assumed (i.e. an IL6 level of 115 pg/ml in the RR group compared with 100 pg/ml in the RL group).
- The correlation between 2 measurements of interleukin 6 in the same subject was set at 0.85. This correlation was estimated by the manufacturer at 0.89, but we have chosen to adopt a slightly lower value, as a conservative approach.
- The errors of the first and second kind were set at 5% and 10% respectively.

If the trial were planned with a single interleukin 6 assay, it would be necessary to include 151 patients per group.

Taking into account a measurement of interleukin 6 at inclusion, and considering that the correlation between the assessments at inclusion and at H32 was 0.85, the number of patients was reduced to 42 per group.

Taking into account the fact that there were 2 intermediate assessments (H12, H24), and that the correlation between the assessments was 0.85, the number of patients was reduced to 25 per arm.

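### Infection treated before the H18–H24 draw could serve as a prespecified covariate for IL-6, but the plan calls stratification impossible and names no covariate (minor; precision only)

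*Combined protocol and SAP*

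**What the plan says.** - **Reason for not stratifying.** Section IV.A.1 (Primary endpoint) expects many infectious complications, inhalation pneumonitis in particular, and explains the design choice thus: "given that it is not possible to perform a stratification on this pathology which nevertheless modifies the rates of IL6".
- **Remedy offered.** The same section will record these complications so that the similarity of the groups can be checked. It says the sizing hypotheses already allow for infection because the source study included infected patients. It also says late infections may be linked to the allocated rewarming rate.
- **Randomisation.** Under Prize draw: "No stratification factors will be taken into account". Under Conduct of the study, Inclusion, on the timing of the draw: "This time window will therefore be between H18 and H24".
- **Samples.** IL-6 is taken at H0, H12 and H24, then at H32, H40 and H48. The temperature target is changed at H24, so the first three samples precede rewarming.
- **Recognising pneumonitis.** Under Management of expected adverse events, doctors receive a procedure "including the anamnestic, clinical, biological and radiographic data that should suggest inhalation pneumonitis", with a recommendation on antibiotics. The flow chart lists treatments administered from J0.
- **Analysis.** Statistics, section A, plans a descriptive comparison of the groups without tests. It then says "The primary endpoint will be analysed using a linear mixed model", with transformation if necessary. Statistics, section E, finalises the analysis plan when the database is frozen.

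**The concern.** Stratifying on infection would indeed be hard if patients were randomised at admission. Here they are randomised 18 to 24 hours after reaching 33°C. Whether treatment for suspected inhalation pneumonitis has begun by then is a yes/no fact that the allocated rate cannot affect. The reason given for setting infection aside therefore does not cover infections already identified at the draw.

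Recording infections and comparing the groups descriptively would reveal an imbalance but leave it in the estimate. With about 25 patients per arm, a factor that the plan itself says changes the endpoint would stay in the error term.

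A second risk concerns timing. If covariates are chosen late, from a general infection record, infections before the draw could be mixed with infections after it. The plan accepts that the latter may depend on the allocated rate, so they are not baseline factors.

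**Working it through.** **Inputs from Statistics, section B.** "The standard deviation of the interleukin 6 assay was set at 40 pg/ml"; "an IL6 level of 115 pg/ml in the RR group compared with 100 pg/ml in the RL group", a difference of 15 pg/ml; "The correlation between 2 measurements of interleukin 6 in the same subject was set at 0.85"; errors of 5% and 10%.

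**The plan's own figures.**
- Single assay: 2 × (40 × (1.960 + 1.282)/15)² ≈ 149.4 by the normal formula and 150.4 by the t-based one, so 151 as stated. This is two-sided; one-sided would give 122.
- One baseline value: 151 × (1 − 0.85²) = 151 × 0.2775 = 41.9, so 42 as stated.
- Repeated measures, with p earlier and q later values: factor = (1 + (q−1)ρ)/q − pρ²/(1 + (p−1)ρ). For p = 1, q = 3 this is 0.1775, and 151 × 0.1775 = 26.8, so 27 against the plan's 25. The sizing is reproduced to within two patients.

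**Inputs the documents do not give (assumptions).** The share of patients treated for infection before the draw is taken as 30–50%. The infection effect d on later IL-6, beyond what the pre-draw IL-6 values in the model predict, is taken as 5, 10 or 20 pg/ml.

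**Residual variance** of the mean of H32, H40 and H48 after adjusting for pre-draw IL-6, with variance 40² = 1600:
- One value: 1600 × (0.9 − 0.7225) = 284.
- Two values: 1600 × (0.9 − 2 × 0.7225/1.85) ≈ 190.
- Three values: 1600 × (0.9 − 3 × 0.7225/2.70) ≈ 156.

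**Variance removed by the infection covariate** is share × (1 − share) × d². Over shares of 30–50% this is 5–6 for d = 5, 21–25 for d = 10, and 84–100 for d = 20.

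**Power** for a difference of 15 pg/ml with 25 per arm: two-sided 5% noncentral t, 48 degrees of freedom, noncentrality 15/√(2V/25), where V is the residual variance.

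| Pre-draw IL-6 values in model | V | No infection term | d = 5 | d = 10 | d = 20 |
|---|---|---|---|---|---|
| One, ρ = 0.85 | 284 | 86.9% | about 87.6% | 89.3–89.8% | 95.7–96.9% |
| Two, ρ = 0.85 | 190 | 96.5% | 96.9% | 97.9–98.1% | over 99.8% |
| Three, ρ = 0.85 | 156 | 98.6% | 98.9% | 99.4–99.5% | about 100% |
| Three, ρ = 0.70 (illustration) | 300 | 85.1% | 85.7–85.8% | 87.5–88.0% | 94.2–95.7% |

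The last row uses V = 1600 × (0.8 − 3 × 0.49/2.4) = 300. It shows that the small gain with three values depends on the correlation being as high as assumed.

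**Chance imbalance.** With 25 per arm and no stratification, the probability that the arms differ by 5 or more infected patients (20 points) is 16.4%, 19.3% and 20.3% at prevalences of 30%, 40% and 50%. Without baseline adjustment, such an imbalance shifts the IL-6 difference by 0.2 × d, which is 2–4 pg/ml for a raw infection effect of 10–20 pg/ml (13–27% of the 15 pg/ml sought). If infection raises IL-6 equally before and after the draw, adjusting for one pre-draw value leaves 0.2 × d × (1 − 0.85) = 0.3–0.6 pg/ml. Adjusting for three leaves 0.2 × d × (1 − 3 × 0.85/2.70) = 0.1–0.2 pg/ml. If infection raises IL-6 only after the pre-draw samples used, the full shift remains.

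**The case against.** The strongest reply is that the pre-rewarming IL-6 samples already do most of the work. An infection treated before the draw should usually show in the H24 value, and often in H12. With all three values in the model, power is 98.6% on the plan's own inputs, so an infection covariate has little left to explain. At d = 20 it would have to account for 54–64% of the remaining variance (84/156 to 100/156), which nothing in the documents supports. This stands and limits the size of the point. It does not remove the point, because the analysis text does not name pre-draw IL-6 as a covariate either.

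Three further points stand:
- The plan says its sizing hypotheses come from a study that included infected patients. A reader might infer that infection was forgotten in the sizing; the documents say otherwise.
- A reader might infer that the plan refuses adjustment. It is silent, and the analysis plan is still to be finalised.
- A reader might infer that unstratified randomisation biases the primary comparison. It does not. Chance imbalance is random error already reflected in the standard error and the 5% test.

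Early pneumonia is also hard to diagnose during cooling, and starting antibiotics partly reflects clinician practice. If nearly all patients or very few were treated, the item would carry little information. The flow chart does not say that antibiotics, their indication or their start time are recorded. These are reasons for a modest claim. They do not make infection unusable, since misclassification of an item fixed before allocation weakens the gain without introducing bias.

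**Conclusion.** The point holds as a minor one about precision. The plan's statement that stratification cannot be done is too broad for a draw at H18–H24, and the primary model should name its baseline covariates. Both the prevalence of infection at the draw and its effect on IL-6 are assumptions. Over the range used, the gain is under 1 point to about 10 points of power if one pre-draw IL-6 value is in the model, and at most about 1.4 points if all three are and the correlation is 0.85. At a correlation of 0.70 the gain with three values could again reach about 10 points.

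A reader might take the rise from 87% to 97% as the expected benefit. That figure needs the largest assumed effect and leaves H12 and H24 unused. A reader might also conclude that the trial should stratify. Omitting stratification for about 50 randomised patients in one centre is an ordinary choice, and a covariate is enough.

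**What to change.** - In Statistics, section A, before database freeze, state that the primary IL-6 mixed model adjusts for pre-rewarming IL-6 (H0, H12, H24) and for infection treated before the draw (yes/no), with the interaction of the infection term with time.
- State that the model does not adjust for infection arising after the draw, because IV.A.1 says this may depend on the allocated rate.
- Add the yes/no item, with the time treatment started, to the eCRF randomisation form, completed before the allocation is shown.
- In IV.A.1, limit the statement that stratification cannot be done to infections not identifiable by the time of the draw.

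The cost is one eCRF entry with its timing, a few lines of analysis text and a few degrees of freedom. Some misclassification is to be expected. Randomisation and patient care do not change.

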 - Bolus of non-depolarising curares: cisatracurium besilate (Nimbex®) bolus 0.1mg/kg, atracurium besilate (Tracrium®) bolus 0.5mg/kg
- Level 3 treatment for chills :
 - After failure of level 2
 - Bolus and maintenance of non-depolarising curares with monitoring of the BSAS score for a target ≤ 1 : cisatracurium besilate (Nimbex®) boli 0.1mg/kg then 10mg/h with increase and decrease in steps of 1mg/h with a target BSAS score ≤ 1 . If a curare infusion is started, it can be stopped once the warming phase has begun and a temperature of 35°C has been reached.

d) Management strategy for targeted temperature control between 32.5 and 33.5°C

Targeted temperature control between 32.5 and 33.5°C will be achieved using an external thermal regulation device of the ArticSun type (BARD, Louisville, Colorado, USA). The protocol will enable a number of parameters to be standardised: sedation, possible curarisation, management of expected adverse effects.

Indeed, although there are numerous methods available to date, none of which has demonstrated its superiority in achieving targeted temperature control between 32.5 and 33.5°C in the management of RTA (active external cooling (15, 16, 81-83)active internal cooling (84, 85)internal cooling with infusion of ice-cold isotonic saline solution (81, 86)), the active external device allows continuous control of temperature and the desired rate of rewarming, which is the subject of this study. In addition, the intensive care unit at La Roche Sur Yon already uses this type of device to perform the 32.5-33.5° CCT, and has the technical expertise to use it routinely.

The implementation protocol for CCT 32.5-33.5 breaks down as follows:

- Rapid intravenous injection of 1500 ml of isotonic saline at 4°C. This technique enables the target temperature to be reached rapidly, with a high safety profile (81, 87).
- After fitting the specific pads, induction continued and hypothermia was maintained at a target temperature of 33°C (allowing the same target temperature to be chosen for the 2 randomisation groups) for 24 hours.
- H0 is defined as the time at which the patient's body temperature reaches 33°C. Taking the sample.
- H12: sample taken
- Time window H18-H24: randomisation via the eCRF.
- H24: sampling and modification of the target internal temperature according to the software for a target of 37°C with a heating rate set according to the randomisation group (0.5°C/h for RR or 0.25°C/h for RL).

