These documents are :

- Protocols and annexes, any amendments,
- Information leaflets and objection forms
- Individual data (authenticated copies of raw data),
- Follow-up documents,
- Statistical analysis,
- Final report of the study.

At the end of the period of practical use, all the documents to be archived, as defined in the CHD Vendée's procedure for filing and archiving documents relating to biomedical research, will be transferred to the archiving site (CHD Vendée Clinical Research Centre) and will be placed under the responsibility of the establishment responsible for the research for 15 years after the end of the study, in accordance with institutional practices.

They may not be moved or destroyed without the agreement of the institution responsible for the research. At the end of the 15-year period, the institution responsible for the research will be consulted for destruction. All data, documents and reports may be audited or inspected.

XI. Financing and insurance

A. Study budget

Insofar as this trial is a routine care study, medical procedures will not be reimbursed. The expected duration of the study is 3 years for 1 centre. The unit cost grid by profession published and updated by the DGOS Bureau PF4 in 2014 was used. Thus, the costs associated with this research are as follows:

Estimate based on 50 randomised patients.

- Time for the psychologist to carry out blind telephone interviews with the randomisation group at D90 (2 hours for 50 patients at €38/hour) 3 800 €
- Data management :

• Data management time :	8 000 €
• Statistical analysis :	4 000 €
• Stationery for information and opt-out letters to patients or their relatives, bedside monitoring sheets :	
500 €	
• Transport of samples from local laboratories to the centralised laboratory :	200 €
• Biology analyses :	
• Cytokine assays at the rate of 6 assays per patient for 50 patients, i.e. 300 assays:	
	13 414 €
• Oxidative stress testing at a rate of 6 tests per patient for 50 patients:	
	4 500 €
• Presentation of results (conference) :	500 €

The total cost is estimated at **34,914** euros.

B. Insurance

Insofar as the research is qualified as Research in routine care by the requested CPP, which means that there is no additional risk associated with the study, the insurance will be that of the establishment responsible for the care (article L. 1142-2).

XII. Feasibility of the study

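### The cut from 42 to 25 per arm counts samples taken before rewarming; the H32 comparison named in the calculation needs about 30 per arm, and power for the 48-hour endpoint is not derived

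*Combined protocol and SAP*

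**What the plan says.** The calculation is in the Statistics chapter, section B (expected number of people). Its inputs are an IL6 standard deviation of 40 pg/ml, means of 115 against 100 pg/ml, a within-subject correlation of 0.85, and type I and II errors of 5% and 10%. It proceeds in three steps:

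- One assay per patient: 151 per group.
- Adding a measurement at inclusion, "considering that the correlation between the assessments at inclusion and at H32 was 0.85": 42 per group.
- In the last step "the number of patients was reduced to 25 per arm". The ground given for this is: "Taking into account the fact that there were 2 intermediate assessments (H12, H24), and that the correlation between the assessments was 0.85".

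The budget section uses the result: "Estimate based on 50 randomised patients".

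The timing is fixed elsewhere. Under Experimental design, both groups receive the same cooling and 24-hour maintenance, and only then do the rates differ. Under Conduct of the study (Inclusion), on randomisation: "This time window will therefore be between H18 and H24". In the temperature-control strategy, the rate is first set here: "H24: sampling and modification of the target internal temperature according to the software for a target of 37°C". Further samples follow at H32, H40 and H48.

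The primary endpoint (Research design, section A.1) is the change in serum IL6 over the 48 hours after 33°C is reached. The analysis is given in one line, plus a remark that data may be transformed: "The primary endpoint will be analysed using a linear mixed model".

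**The concern.** Extra measurements reduce the sample size in one of two ways. As additional baselines they explain more of the outcome variance. As additional outcomes they are averaged, but each must then carry the treatment difference. H12 precedes randomisation and H24 is taken as the rate is changed, so neither can carry a rewarming effect. The reduction to 25 therefore has to be justified with both as baselines.

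This paragraph is the only justification for 25 randomised per arm, for the 60 inclusions and for the 50-patient budget. No interim analysis is planned, so nothing later would reveal a sizing problem. If the 90% power does not hold for the one outcome time named, and was never derived for the 48-hour endpoint, a null result cannot be read against it.

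**Working it through.** **Inputs**, all from the sample size section: SD 40, difference 15, rho 0.85 between any two measurements, alpha 5%, power 90%. Sidedness is not stated; two-sided is inferred, because a one-sided test would need 122 per group, not 151.

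**Step 1, single assay.** n = 2 × (1.960 + 1.282)² × (40/15)² = 149.4, so 150 per group by the normal approximation. The t-test version gives 151. The plan's figure reproduces.

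**Step 2, one baseline and H32.** 151 × (1 − 0.85²) = 151 × 0.2775 = 41.9, so 42. The plan's figure reproduces.

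**Step 3.** With p baselines and r averaged outcomes, and the same correlation between all pairs of times, the variance factor is

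factor = [1 + (r − 1)rho]/r − p·rho²/[1 + (p − 1)rho].

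| Role of the samples | p | r | Factor | 151 × factor |
|---|---|---|---|---|
| H0 baseline; H12, H24, H32 as outcomes | 1 | 3 | 0.1775 | 26.8 |
| H0 baseline; four outcomes | 1 | 4 | 0.1650 | 24.9 |
| H0, H12, H24 baselines; H32 outcome | 3 | 1 | 0.1972 | 29.8 |
| H0, H12, H24 baselines; mean of H32, H40, H48 | 3 | 3 | 0.0972 | 14.7 |

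The third row matches the design and the outcome time named: 1 − 3 × 0.7225/2.70 = 0.1972, so 30 per arm (31 by an exact t calculation). The first row gives 27, not 25, and assumes the full 15 pg/ml difference before rewarming. The second row gives 25, but needs a fourth outcome that the text does not name.

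**Power at 25 per arm for H32.** The residual SD is 40 × √0.1972 = 17.76 and the standard error of the difference is 17.76 × √(2/25) = 5.02. The ratio 15/5.02 = 2.99 gives 84.7% power (normal) or 83.3% (noncentral t).

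**Power at 25 per arm for the 48-hour data.** The documents give no effect profile, so the three below are illustrative assumptions, all with three baselines and rho 0.85 throughout.

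| Assumed 15 pg/ml difference | Average over H32–H48 | Power for the mean (t / normal) | n per arm for 90% (mean) | Power of joint 3-df test (F / chi-square) |
|---|---|---|---|---|
| At all three times | 15 | 98.6% / 98.9% | 14.7 | 94.2% / 96.0% |
| At two of three | 10 | 79.3% / 80.9% | 33.0 | 90.7% / 93.2% |
| At H32 only | 5 | 28.4% / 29.4% | 132.1 | 71.1% / 75.3% |

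**Sensitivity to the correlation** (assumed values, 25 per arm, normal approximation). For H32 alone, power is 57% at constant rho 0.70, 74% at 0.80 and 94% at 0.89, the manufacturer's value quoted in the plan. If instead correlation decays by 0.85 per sampling step, H32 alone has 71% power and needs about 42 per arm; the H32–H48 mean with a sustained difference has 62% and needs about 52.

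**The case against.** The best defence is that 25 is not an arithmetic slip: the same formula yields 24.9 with one baseline and four outcomes. That may be how the figure arose. It does not help, because the section names only H12, H24 and H32 after inclusion, and the route still uses samples taken before rewarming as outcomes carrying the full effect. The fault lies in the role given to those samples.

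A second defence is that H32 alone is not the primary endpoint. The plan gives one mean level per group for a repeatedly measured outcome, so a sustained 15 pg/ml difference is a natural reading. On that reading about 15 per arm suffice, and 25 is more than enough. This stands as far as it goes: the trial is not shown to be underpowered. But the plan does not state a sustained difference or a contrast over H32–H48, and the calculation uses neither H40 nor H48. The less favourable profiles are likewise not in the documents, and the lowest figure pairs an effect at one time with a contrast that dilutes it.

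Third, 83–85% depends on rho being 0.85 between every pair of times. That is correct, and the sensitivity range is wide. It is, however, the plan's own input, used for the 42 and the 25 alike.

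Finally, the contrast may be left to a separate analysis plan. The Statistics chapter refers to a pre-established plan, finalised when the database is frozen, but the text available gives no contrast, and a sample size needs one beforehand.

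**Conclusion.** The point holds. Under the plan's own SD, difference and constant correlation, and a two-sided 5% test, the only outcome time named in the calculation needs about 30 per arm for 90% power. At 25 per arm the type II error there is about 15–17%, against the stated 10%. For the 48-hour mixed model no power has been calculated. With those inputs it could be near 99% or well below 90%, depending on the contrast, the differences at H32, H40 and H48, and whether the correlation stays constant. The plan sets out neither the contrast nor the differences over time. The conclusion is that the stated power is unsupported, not that the trial is too small.

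**What to change.** Replace the paragraph that reaches 25 with a calculation for the actual primary contrast. It should treat H0, H12 and H24 as baselines, name the time points after the start of rewarming, give the assumed difference at each, state the formula and the correlation structure, and report power at about 25 randomised per arm, with a range over the correlation. The mixed-model description should name the same contrast and baseline handling. Which contrast to use is the sponsor's choice. If H32 alone remains the planning comparison, restate power as about 83–85% at rho 0.85.

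The cost is one rewritten paragraph and possibly a less favourable stated power. More patients are not necessarily required: a constant difference over H32–H48 with constant correlation needs no increase, whereas keeping 90% for H32 alone needs about 30 randomised per arm.
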